Identifiable research data, including recruitment and screening information and code keys, are stored on a secure database located on the internal PET Center Network. The PET network is protected by a Cisco PIX firewall operated by ITS. All research data are backed up nightly to a Dell PV-136T library with 4 IBM Ultrium-TD2 tape drives using the backup software Legato Networker 7.3 from EMC. Human subjects enrolled in the study are assigned a subject-specific random identifier. Subject identifiers and the means to link the subject names and codes with the research data are stored in separate locations within the database. The software of the database limits the ability to connect the random identifier to the actual subject identification information to those members of the research team who have direct contact with the research subjects, such as physicians, research nurses, and technologists. Access to the database is password protected and each research team member is required to have a unique ID and password to gain access to the database. Authorized users employ their netid, and authentication is performed using Yale's central authentication server. Users always access research data through the random identifier only. Direct identifiers belonging to subjects who withdraw from the study will be stripped from the key.

e. What mechanisms are in place to ensure the proper use and continued protection of these data after the subject participation in the study has ceased?

Procedures to ensure confidentiality follow the regulations and policies of Yale School of Medicine. The security measures in 4d will continue to be in place to protect study data.

f. What will be done with the data when the research is completed? Are there plans to destroy the identifiable data? If yes, describe how, by whom and when identifiers will be destroyed. If no, describe how the data and/or identifiers will be secured.

Study data will be archived in a secure storage facility, data will not be destroyed.

g. Who will have access to the protected health information? (such as the research sponsor, the investigator, the research staff, all research monitors, FDA, QUACS, SSC, etc.)

The PI, study personnel and the Department of Psychiatry Business Office

h. Which external or internal individuals or agencies (such as the study sponsor, FDA, QUACS, SSC, etc.) will have access to the study data?

Internal: Principal investigators and their respective research teams, YCCI Hospital Research Unit, CMU, PET and MRI centers, Y-NHH Radiation Safety Committee (RSC) and Yale University RSC.

i. If appropriate, has a Certificate of Confidentiality been

obtained? A certificate has been obtained from NIAAA

- j Are there any mandatory reporting requirements? (Incidents of child abuse, elderly abuse, communicable diseases, etc.)

Child abuse, elder abuse and intent to harm self or others.

5. **Potential Benefits:** Identify any benefits that may be reasonably expected to result from the research, either to the subject(s) or to society at large. (Payment of subjects is not considered a benefit in this context of the risk benefit assessment.)

This study will not directly benefit the participants. The results of this laboratory-based drinking paradigm with high resolution PET imaging before and after naltrexone treatment will shed new light on the actions of NTX and the dynorphin/KOR system in alcohol drinking behavior. An additional benefit to subjects is that they will be offered feedback about their drinking and active referral to treatment for their alcohol problems should they so desire. Most alcohol abusers have impairments in their psychosocial functioning as a result of their drinking and can benefit from treatment. The proposed study may be a conduit for some to receive treatment and for others to reduce their drinking on their own. Although the direct benefit is not great for subjects, given the potential benefit to developing effective treatments for alcoholism, the risk-benefit ratio appears favorable.

SECTION X: RESEARCH ALTERNATIVES AND ECONOMIC CONSIDERATIONS

1. **Alternatives:** What other alternatives are available to the study subjects outside of the research?
 NA-This is not a treatment study. However, participants will be provided with a motivational interview upon completion of the inpatient and outpatient portions of this study to provide feedback on their drinking. If they request a referral for treatment to cut back or quit drinking at this time, we will provide them with referral options.
2. **Payments for Participation (Economic Considerations):** Describe any payments that will be made to subjects, the amount and schedule of payments, and the conditions for receiving this compensation.

Heavy Drinkers: Because this study may not have direct benefits to the individual participant, subjects will be offered payment for their participation. Subjects will have the opportunity to receive \$50 for the initial interview, \$50 for the physical examination, \$250 for the first PET scan, \$450 for the second PET scan and \$50 for the MRI. Subjects will also receive \$150 for participating in the first drinking paradigm, \$10 per day (up to 11 days) for transportation to our clinic for daily medication dose, \$170 for taking medication on all days, \$250 for participating in the second lab drinking paradigm, and \$30 for completing a one week follow up. In addition, all subjects will have the opportunity to earn an extra \$36 (depending on their drink consumption) during each of the ADP sessions and \$30 for computer assessments at each of the ADP sessions. Additionally, in the case that the first arterial line cannot be placed at the first PET scan, participants will be paid \$50 and rescheduled. In the event that a participant is asked to come back in for a repeat lab appointment (bloodwork or EKG) he/she will be paid \$25. In the event that the participant serves as a standby for ADP/PET 1, he/she will be paid \$50. In the event that a participant needs a repeat MRI, he/she will be paid \$50. In the event that a participant needs to complete an extra overnight visit on the evening prior to a rescheduled PET

scan, he/she will be paid \$100. That is a possible total of \$2017, for attending and participating in all appointments.

An additional benefit to subjects is that they will be offered feedback about their drinking and active referral to treatment for their alcohol problems should they so desire. Most alcohol abusers have impairments in their psychosocial functioning as a result of their drinking and can benefit from treatment. The proposed study may be a conduit for some to receive treatment and for others to reduce their drinking on their own.

This progressively increasing payment structure was developed in order to motivate subjects to complete all phases of the study, since obtaining complete data in this within-subject crossover study is the key to achieving the goals of the project. We are trying to avoid early drop out by using increasing incentives for completion of the entire study.

Healthy controls: Healthy controls will be paid \$50 for the initial interview, \$50 for the physical examination, \$250 for the PET scan, and \$50 for the MRI. Additionally, in the case that the first arterial line cannot be placed at the PET scan, participants will be paid \$50 and rescheduled. In the event that a participant is asked to come back in for a repeat lab appointment (bloodwork or EKG) he/she will be paid \$25. In the event that the participant serves as a standby for a PET scan, he/she will be paid \$50. In the event that a participant needs a repeat MRI, he/she will be paid \$50. That is a possible total of \$575 for attending and participating in all appointments.

3. **Costs for Participation (Economic Considerations):** Clearly describe the subject's costs associated with participation in the research, and the interventions or procedures of the study that will be provided at no cost to subjects.

The subject will incur no costs to participate in this research and will receive a full physical exam at no cost.

4. **In Case of Injury:** This section is required for any research involving more than minimal risk.
- Will medical treatment be available if research-related injury occurs? Yes, but injury is unlikely
 - Where and from whom may treatment be obtained? Treatment may be provided by Yale- New Haven Hospital or any health care provider chosen by the study subjects.
 - Are there any limits to the treatment being provided? Limits to treatment may be imposed by the insurance carrier of the study subjects.
 - Who will pay for this treatment? The study participant or their insurance carrier will be expected to pay for the cost of the treatment. No additional financial compensation for injury or lost wages is available.
 - How will the medical treatment be accessed by subjects? The study team will provide assistance to the subjects in accessing medical treatment through referrals, or the study subjects may choose to access treatment on their own.

References

- O'Malley, S.S., A.J. Jaffe, G. Chang, R.S. Schottenfeld, R.E. Meyer, and B. Rounsaville, *Naltrexone and coping skills therapy for alcohol dependence. A controlled study.* Arch Gen Psychiatry, 1992. 49(11): p. 881-7.
- O'Malley, S.S., S. [name], C. Farren, R. Sinha, and M.J. Kreek, *Naltrexone decreases craving and alcohol self-administration in alcohol-dependent subjects and activates the hypothalamo-pituitary-adrenocortical axis.* Psychopharmacology (Berl),

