Our project will investigate a provocative finding in alcohol treatment research [3]. Namely, that FH of alcoholism may influence (or be a marker of an underlying trait that influences) the response of heavy drinkers (HD) to NTX. Simply put, not every HD responds favorably to NTX but lower levels of drinking can be achieved and risk of relapse is diminished in some. It is essential for clinical treatment and future drug development to understand how NTX works. Preclinical results have implicated kappa in *changes* in alcohol drinking, but the directionality of these changes are complex. We propose that the differential efficacy of naltrexone may be related to differences in occupancy of kappa opioid receptors by naltrexone. This translational project will test this hypothesis. The results of this project could not only help maximize treatment effectiveness of naltrexone but also result in identification of new medication treatment targets for more optimal reduction of alcohol drinking.

3. Research Plan: Provide an orderly scientific description of the study design and research procedures as they directly affect the subjects.

A total of 56 HD subjects will be tested; equal numbers of FHP and FHN subjects will be recruited. Data from the first year's subjects ("initial cohort" perhaps specify how many will be used for this purpose) will be analyzed prior to scanning the remaining subjects in order to address aims S2 and S3 (identification and validation of a reference region; reduction in scan duration) which are addressed below in PET methods.

Study design: Because we are interested in investigating the implications of baseline KOR, as well as Occupancy of KOR by NTX, we must perform 2 PET scans on each subject; one at

baseline and one following 5-11 days of NTX pretreatment. Similarly, because we are interested in relating responsivity to occupancy of KOR by NTX we must make two assessments of drinking behavior using the ADP; one at baseline the day before or after the first PET scan and one following 5-11 days of treatment with NTX. The post PET scan and post ADP will ideally take place on Day 6 or Day 7 of medication, but we will allow up to 11 days of medication for scheduling issues and the possibility that the appointments will be within this time frame. All

In designing the study, we had to balance various competing interests and we provide justifications below:

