- a. Lack of Placebo and use of within subjects design: We considered including a placebo control. But then in order to control for “order” effects, we would have had to randomize placebo and NTX conditions AND allow a significant washout period between medication conditions, especially for those receiving NTX first. This would have led to problems with retention and increased the sample size. We also considered a between subjects design but this would have also increased sample size and costs. Therefore, in order to contain costs and increase feasibility, we decided to use a within subjects design examining a change from baseline, and configured the overall duration of participation to be as close to a single week as possible. While our proposed design could still have “order” effects we do not believe that it will influence our ability to detect an initial signal.
- b. Use of Mock ADP and PET sessions: To minimize the possible stress and novelty associated with a first PET scan and the ADP sessions, as time and scheduling permits, we will conduct a mock PET scan and a walk-through of the ADP procedures prior to the baseline PET and ADP. During the mock PET session, the subject will lie in a replica of the PET scanner, be told when the scanner is being “turned on” and when blood samples are “being drawn”. During the mock ADP session, participants will be exposed to the HRU rooms in YNHH where the ADP’s are conducted and will be walked through the ADP procedures.
- c. Timing of PET scan: The preliminary PET test/retest data suggest that BP_{ND} for our new KOR tracer may be higher in the afternoon (Figure 6). (Note: This *cannot be* explained by a carryover effect of a high-mass injection of tracer in the morning (test) scan, since that would cause BP_{ND} to be lower in the second scan.) We speculate that this effect could be due to diurnal fluctuations in dynorphin level. Regardless, we will control for it by scheduling each scan at approximately the same time of day (around mid-day).

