Ten minutes prior to the start of the priming dose (PD) period (i.e., 2:50 pm), the research assistant will walk into the participant's room with the glasses, the alcohol, and the mixers. The research assistant will then proceed with the mixing of the priming drink of alcohol in front of the participant. When done, he/she will leave the drink on the table, instruct the participant not to consume the priming drink until they are told to do so and leave the room.

Priming dose (PD) period

The PD of alcohol will be provided at 3 pm to model a "lapse" situation and subjects will have 5 minutes to drink it. A 40 minute absorption period will follow during which the alcohol craving (AUQ; [45]), stimulation/sedation (BAES; [46]) and physiological effects (heart rate, blood pressure, breath alcohol levels) of this priming dose of alcohol will be monitored every 10 minutes.

Alcohol self-administration (SA) periods

Following the PD, participants will be exposed to three one-hour SA periods designed to model a

“relapse” situation. During each SA period they will be permitted to drink up to four alcoholic drinks designed to raise Blood Alcohol Level (BAL) by 0.015 mg% of alcohol, or to receive cash (equivalent to the price of each drink that is not consumed). The first SA period will begin at 4 pm, when the research assistant will take 4 prepared drinks into the room along with a "tab" sheet worth \$12. The participant will be informed that these 4 drinks will be available to him/her for the next 60 minutes (i.e., until 5 pm). S/he can choose either to drink or to keep the money; each drink will cost \$3. For example, if the participant chooses to drink only one drink in the next one hour, s/he will earn \$9. The money will be given to them the next morning before they leave the hospital. The second and third SA periods will begin at 5 pm and 6 pm, respectively, and will be similar to the SA period. Thus, participants can choose to consume up to 12 additional drinks over this 3 hour period or to receive up to \$36 to take home the next morning. Number of drinks that each participant consumes during this period will serve as the primary outcome for this portion of the experiment.

❖ *Beverage content and mixers*

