Primary Aim 1. Occupancy of KOR by NTX and drinking. This aim seeks to determine the degree to which occupancy of kappa by NTX mediates responsivity to NTX in heavy drinkers. Responsivity to NTX is defined as the change in the total number of drinks consumed in the NTX ADP versus the baseline ADP. Tests for mediation will be conducted using the regression strategies described initially Baron and Kenny [53], and the more recent elaboration by Kraemer et al. [54]. The proposed mediator (i.e., the potential mechanism of change), occupancy of KORs, is measured as the fractional change in BP_{ND} before and after treatment with NTX. The analyses will determine whether occupancy is associated with a) NTX treatment, and b) NTX responsivity.

Primary Aim 2. Family History of Alcoholism as a moderator: This aim seeks to determine if the relationship between NTX responsivity and occupancy of KOR is altered by FH status. FHP and FHN will be compared on NTX responsivity and occupancy of KOR. Tests for moderation will be conducted using the strategies described by Baron and Kenny [53], and the elaborated by Kraemer et al. [54]. The primary tests will be whether there is a significant FH by dose interaction on NTX response and occupancy of KOR.

Secondary Aim 1. Baseline KOR differences. This aim seeks to determine if baseline levels of KOR differ between FHP and FHN heavy drinkers, and are related to either drinking in baseline or NTX ADP. FHP and FHN groups will be compared using chi-square tests for categorical variables, and using t-tests or Mann-Whitney tests for continuous variables. All continuous variables will be examined for adherence to the normal distribution using normal probability plots and Kolmogorov-Smirnov tests. If normality is not satisfied and transformations do not help with achieving normality, alternative analytic strategies will be considered such as generalized estimating equations or nonparametric methods. The relationship between baseline KOR and drinking will be examined via Pearson product-moment correlations.

Secondary Aims 2 and 3. Scan duration and reference region. We will look for correlations between BP_{ND} estimates based on 2T model with full AIF and all data vs alternative models and data ranges. Group variances in baseline KOR at or lower than 2T estimates will permit adoption of simpler models.

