The alcohol challenges will be conducted by personnel experienced in alcohol challenge research. As described above, all subjects will be under supervision to prevent possible accidents. At the end of the challenge session all subjects will be kept in the HRU where they will stay overnight to prevent the possibility that they would continue drinking after the session and place themselves at risk of accidents. Although we have never had a subject chose to leave a session early, should a subject insist on leaving the research setting prematurely, we will provide transportation back to their residence. This contingency is explicitly addressed in the consent form. Clearly, subjects are free to discontinue the experiment at any time. However, if a subject chose to discontinue participation after alcohol has been administered we will require them to stay in the HRU until their blood alcohol level is below 0.04 and they will then be provided with a ride home. Furthermore, at the Principal Investigator's discretion, a participant will be discontinued if he/she does not drink any of the choice drinks at ADP 1. This absence of drinking creates a floor effect and does not allow for evaluation of change in drinking behavior at ADP 2 after taking study medication. Given the cost of the scan and the hospital visit, it does not seem reasonable to continue participants whose data will not be meaningful. Participants will be told that the study doctor may discontinue his/her participation if they think you are not responding well to the medication.

3) Research Records:

Right to privacy for participation in this research will be protected through anonymous coding of data and proper storage of research records. Access will be limited to the PI and her designates involved in the study. A certificate of confidentiality has been obtained from NIAAA. Safeguards include screening by experienced professionals in order to ensure that the inclusion and exclusion criteria are met before patients are entered in the study, including physical exam and laboratory tests.

4) Risks Associated with Blood Drawing:

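### Participants are told they may be dropped for poor response to the medication; this does not match the zero-drink rule beside it and may cue fewer drinks at the naltrexone session

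*Combined protocol and SAP*

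**What the plan says.** Section IX, 2. Minimizing Risks, item 2) Alcohol Challenges, contains one discontinuation rule tied to drinking. At the investigator's discretion, "a participant will be discontinued if he/she does not drink any of the choice drinks at ADP 1". The reason given is statistical: "This absence of drinking creates a floor effect and does not allow for evaluation of change in drinking behavior at ADP 2 after taking study" [drug]. The same paragraph closes with what participants hear: "Participants will be told that the study doctor may discontinue his/her participation if they think you are not responding well to the medication".

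The surrounding design is as follows.

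- **Order and timing.** Research Plan, Study design: ADP 1 is the baseline session, and the second ADP is "one following 5-11 days of treatment with NTX".
- **No placebo.** Item a of the design justifications accepts the consequence: "While our proposed design could still have “order” effects we do not believe that it will influence our ability to detect an initial signal".
- **Outcome.** Alcohol self-administration periods: "Number of drinks that each participant consumes during this period will serve as the primary outcome for this portion of the experiment". Statistical Considerations, Primary Aim 1: "Responsivity to NTX is defined as the change in the total number of drinks consumed in the NTX ADP versus the baseline ADP".
- **Payments.** Section X, item 2, describes a rising schedule: "We are trying to avoid early drop out by using increasing incentives for completion of the entire study".
- **Contrary text.** Section IX, Risks, item 8 (Alcohol Withdrawal) says participants will not be asked to change how they drink.

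**The concern.** There are two problems.

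First, the reason given to participants is not the rule described. The rule acts on behaviour at a session held before the first dose, so it cannot concern response to the drug. No section sets a rule for dropping poor responders, and none defines for participants what a good response would be.

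Second, the statement may act as a demand cue. Participants know that the second session is the one on medication, they choose how much to drink there, and they have been told that poor response can end participation. Some may take this to mean that they should drink less. The plan already tries to limit order effects with a walk-through and beverage tasting; this sentence works against that effort.

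At stake is the interpretation of the mean change in drinks from baseline to naltrexone. Reduced drinking on 100 mg is one of the two hypotheses named in the power analysis.

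**Working it through.** **1. Rule and statement side by side**

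| | Rule described | What participants are told |
|---|---|---|
| Trigger | no choice drinks taken | poor response to medication |
| When it can apply | ADP 1, before naltrexone | only after dosing has begun |
| Stated purpose | avoid a floor effect | none given |

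The two cannot be the same rule.

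**2. What response means here.** The Specific Aims and Primary Aim 1 both define responsivity as change in drinks. The sentence stands under Alcohol Challenges, directly after the text on drinking data, and not under the Naltrexone item that deals with side effects.

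**3. Can a cue be separated from the drug?** Write the mean change in drinks as

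mean change = drug effect + cue effect + order effect.

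With one sequence and no placebo period, only the sum is estimated.

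**4. Consequence for a pre-post test (illustration).** The documents give no figure for the cue, so it is assumed. Let the drug effect be zero and let the cue lower drinking by δ standard deviations of the change score in everyone. A paired t-test at two-sided 0.05 has n − 1 degrees of freedom and noncentrality δ√n. The plan names the hypothesis but not this test. Both n = 36 (18 per group; Specific Aims, power analysis) and n = 56 (Research Plan) are used because the documents give both. At δ = 0.2, the noncentrality is 0.2 × √36 = 1.20 or 0.2 × √56 = 1.50.

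| Assumed δ | Rejection rate, n = 36 | Rejection rate, n = 56 |
|---|---|---|
| 0.1 | 9% | 11% |
| 0.2 | 22% | 31% |
| 0.3 | 42% | 60% |
| 0.5 | 83% | 96% |

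**5. Consequence for the family-history contrast.** The contrast is (drug + cue in FHP) − (drug + cue in FHN). An equal cue cancels, and the test stays at 5%. If the cue differs between groups by Δ, the noncentrality is Δ√(n per group / 2). At Δ = 0.2 this is 0.2 × √9 = 0.60 with 18 per group (rejection 9%), or 0.2 × √14 = 0.75 with 28 per group (11%).

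**6. Consequence for the occupancy association.** Cov(occupancy, change) = Cov(occupancy, drug effect) + Cov(occupancy, cue). A constant cue contributes nothing. A cue that varies between people with standard deviation τ, in units of the change-score SD without the cue, and is unrelated to occupancy, shrinks the correlation by 1/√(1 + τ²). For an assumed τ = 0.3 this is 1/√1.09 = 0.96; for τ = 0.5 it is 1/√1.25 = 0.89.

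**7. Money outstanding at ADP 2 (Section X, item 2).** Core payments are interview 50, physical 50, PET 1 250, PET 2 450, MRI 50, ADP 1 150, transport 110, medication 170, ADP 2 250, follow-up 30, tabs 2 × 36 = 72 and computer tasks 2 × 30 = 60:

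50 + 50 + 250 + 450 + 50 + 150 + 110 + 170 + 250 + 30 + 72 + 60 = $1,692.

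The PET scan is mostly scheduled for the morning after the ADP (Research Plan, scheduling of sessions). What then remains is PET 2 and follow-up: 450 + 30 = $480, and 480/1,692 = 28%. If the PET comes first, only the $30 follow-up remains (30/1,692 = 2%). This treats the transport and medication payments as earned by ADP 2 and takes transport at its 11-day maximum.

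**The case against.** The strongest reply is that the cue is conjecture. The sentence sits in a section on minimizing risk and can be read as poor tolerability. The participants are not seeking treatment, no section tells them that a good response means fewer drinks, and item 8 of the Risks says they are not asked to change their drinking. The documents do not say when the statement is made; if it is made at consent, it precedes both sessions. The fixed order without placebo is disclosed and justified, and expectancy would remain if the sentence were deleted.

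Much of this stands. A cue is plausible but not shown, and a reader who infers that the sentence does make people drink less, or that it is an instruction attached only to the on-drug session, goes beyond the documents. What does not fall away is the mismatch in step 1, which needs no assumption about behaviour. The ambiguity between tolerability and drinking is itself a reason to reword, and item 8 shows that the sentence sits badly with the plan's own intent.

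A reader might also count everything paid after ADP 1 and the first PET: 110 + 170 + 250 + 450 + 30 + 36 + 30 = $1,076, or 64% of $1,692. The sum is right but does not fit the mechanism. By the time drinks are chosen at ADP 2, the dosing days have largely passed and the session fee is for taking part. No section makes any payment conditional on response.

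Finally, the emergency-card text (Section VI, Background Information; Section IX, Risks, Naltrexone) reads as if treatment might be unknown. All heavy drinkers receive naltrexone and there is no placebo, so that text should be reconciled too; it does not establish a blind.

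**Conclusion.** The point holds as a wording defect with a possible, unmeasured effect on the outcome. It is certain that the reason told to participants differs from the only drinking-related rule described. It is plausible, not demonstrated, that the wording cues fewer drinks at ADP 2. If it does, the cue cannot be separated from naltrexone in the pre-post change.

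A reader might infer that both primary aims on occupancy and family history are biased. The documents do not support that: a uniform cue leaves the FHP–FHN contrast unbiased, and the occupancy association is biased only if the cue varies with occupancy. Uneven reactions would add noise to both. Nor would a uniform cue act on the FHN group alone; FHP drinkers would shift as well.

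The size in drinks cannot be derived. The rejection rates above rest on an assumed additive shift in SD units, which is approximate because the count is bounded between 0 and 12. The financial stake at ADP 2 is about 28% of core payments when the PET follows the ADP.

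**What to change.** 1. Remove the reference to medication response. Reconcile what participants are told with the rule actually applied, in neutral terms: the study team may end participation after any visit for safety or study-procedure reasons. This need not announce the zero-drink rule, which could itself prompt drinking at ADP 1.
2. Keep any tolerability statement separate and word it as side effects.
3. Read the same script before both ADPs: there is no expected or correct amount to drink, and, apart from the $3-per-drink tab, payment for the session does not depend on how much is drunk or on any effect of the medication. The tab must be excepted because unspent drinks are paid out, up to $36 per session. The script should not promise that continuation is independent of drinking while the zero-drink rule stands.

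Which discontinuation rule is right is left to the investigators. The cost is a few sentences in the protocol, participant information and ADP script, with no change to visits, data or sample size.
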